There will be a few recruitment methods utilized to reach out to potential participants from the Vocational Village. First, inclusion and exclusion criteria will be shared with MDOC, Michican Department of Corrections Leaders and/or Teachers at the Vocational Village. MDOC Vocational Village staff will then identify a list of potential participants. We will then send Leaders and/or teachers a prepared flyer and/or letter to be distributed to those who might be eligible based off of the criteria. MDOC Vocational Village staff will use their own assessments in order to assess age, reading level, COMPAS Risk Assessment, possible impairments, etc. These assessments are for admittance to the Vocational Village as well as inclusion in this research study. After the flyer and/or letter is provided to villagers, study staff will schedule an information session with those identified villagers. The research team will inform villagers about the study during that time.

We will approach everyone who meets these eligibility requirements and will stress to the prison staff that we need to include and approach everyone equally without any "cherry-picking" by administration. We will also stress the voluntary nature of the study and the importance for all prison staff to be impartial. We believe that this method of recruitment will be the most fair in order to reach a wide potential of participants who will be able to utilize the virtual interview tool.

The MDOC administration estimates that we will be able to recruit approximately 60 villagers that meet inclusion criteria within a 12-month recruitment window. Using a 2:1 randomization model, we expect to enroll approximately 40 villagers in the SAU+VR-JIT group and 20 villagers in the SAU-only group. The Vocational Village will have no role in determining which arm participants are enrolled in; that process will be randomized and up to the University of Michigan staff.

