Leaders and Teachers (staff involved in training) at the Vocational Villages will also be recruited to participate. They will assist with identifying potentially eligible villagers, complete some brief surveys, and help assist with teaching the Virtual Interview Training to the villagers. Leaders and Teachers will also sign consent forms if they choose to participate, and will receive a copy of the consent form for their records.

The Principal Investigator will be present at the facilities (SMT and MTU) for first-time data collection visits or whenever new procedures are being implemented. Additionally, senior study team members (full-time study staff who hold a bachelor's or master's degree will be present on all data collection trips within the prison. These are non-student staff members. Everyone will also carry a letter from the MDOC Offender Success Administrator, [name], that states video-recorded participant data are not to be reviewed by MDOC staff on site at SMT and MTU.

D.1 Study Visit 1 & 2: Baseline Data Collection with Village Participants

During the first study visit, study staff will administer consent as previously noted. This process should take about 25 minutes. Next, consented villagers will complete a few short surveys, one on their background, a DSM-5 Level 1 symptom measure, and a brief psychological distress survey (SCL-10-R) [93, 94]. The DSM-5 Level 1 symptom measure was created to aid in a comprehensive mental status assessment by measuring mental health symptoms [93]. The SCL-10-R is a 10-item checklist of psychological distress based on the Symptom Checklist-90 (SCL-90) [93]. They will also complete a practice interview with study staff that will be audio and video recorded. The practice interview can last around 20 minutes. Afterwards, they will complete some self-report measures on their anxiety, motivation, and self-efficacy. Each of these surveys will be about five minutes each. The first study visit should be approximately 75 minutes. These tasks will be divided to two days.

D.2 Village Participants will be randomized into the VR-JIT group or the control group.

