13.0 Data Analysis

H1: SAU+VR-JIT trainees will have higher employment rates than SAU-only by T3. To test H1, we will use multiple logistic regression and a Wald chi-square test of the coefficient to its standard error, to compare the adjusted employment proportions in the two conditions (attained a job = 1 vs. failed to attain a job or censored with a job = 0, between T1 and T3). Our MICHR-funded pilot trial does not have the resources to be an appropriately powered trial but instead we are using this pilot to estimate an effect size to use in a future adequately powered trial.

H2: SAU+VR-JIT trainees will have greater improvement in job-interview skills than SAU-only by T2. To test H2, we will conduct a repeated-measures analysis of variance (RM-ANOVA) with pretest and post-test interview scores as the repeated measures and treatment group as the fixed factor. Our MICHR-funded pilot trial does not have the resources to be an appropriately powered trial but instead we are using this pilot to estimate an effect size to use in a future adequately powered trial.

H3: SAU+VR-JIT trainees will have greater reductions in recidivism than SAU-only between T1 and T3. To test H3, we will compare recidivism percentages between SAU+VR-JIT and SAU-only at T3. Our MICHR-funded pilot trial does not have the resources to be an appropriately powered trial but instead we are using this pilot to estimate an effect size to use in a future adequately powered trial.

2.2.6 Analyses to Test Objective 2 are Based on Corbiere et al.'s [19] Model of Employment H5: Improved interviewing skills will mediate the relationship between VR-JIT (number of completed virtual interviews) and employment outcomes (i.e., obtaining employment). To test H5, we will test first for a significant SAU+VR-JIT impact on interview skills compared with SAU-only, then check for treatment by mediator interaction [81], then evaluate the product of the two coefficients [82] with bootstrapped confidence intervals [83].

Participants, Measures, Procedures, and Analyses.

A mixed-method process evaluation will entail conducting surveys and semi-structured interviews with villagers and teachers.

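### H2 is analysed as a change score by two-time-point RM-ANOVA; ANCOVA on the pre-randomization pretest would usually estimate the same effect more precisely, at no cost

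*Combined protocol and SAP*

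**What the plan says.** Section 13.0 states H2 as "SAU+VR-JIT trainees will have greater improvement in job-interview skills than SAU-only by T2" and tests it with a "repeated-measures analysis of variance (RM-ANOVA) with pretest and post-test interview scores as the repeated measures and treatment group as the fixed factor". It names no baseline covariate, does not say which term of the model answers H2, and gives no effect estimate or confidence interval for it. The same paragraph says the trial is not appropriately powered and that "we are using this pilot to estimate an effect size to use in a future adequately powered trial".

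The pretest interview belongs to baseline data collection (Section 6.0, D.1): "They will also complete a practice interview with study staff that will be audio and video recorded". Randomization is the next step (D.2): "Village Participants will be randomized into the VR-JIT group or the control group". Amendment Ame00101332 moves visits to the telephone but leaves randomization as it was. Both arms repeat the interview at post-test (D.5). Section 4.0 expects "approximately 40 villagers in the SAU+VR-JIT group and 20 villagers in the SAU-only group".

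H5 in Section 13.0 opens with an arm comparison on the same outcome: "we will test first for a significant SAU+VR-JIT impact on interview skills compared with SAU-only".

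**The concern.** H2 speaks of greater improvement, so the term that answers it is group by time. With two time points, that test is a comparison of mean change between arms. A change score subtracts the whole pretest value, whatever the actual relation between pretest and post-test. Unless the slope of post-test on pretest is close to 1, this subtracts too much or too little and leaves avoidable noise in the estimate.

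The trial expects about 20 controls and cannot buy precision with more participants. If its product is an effect size for the next trial, a wider interval than the data require weakens that product directly. The pretest needed to narrow it is already being collected, and before allocation.

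**Working it through.** **Inputs from the documents.** Total N = 60, allocated 2:1 as 40 and 20 (Sections 3.0 and 4.0); one pretest and one post-test (Section 6.0, D.1 and D.5; Section 13.0). The plan states no power or precision figure for H2, so there is none to reproduce.

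**Assumptions, because the documents are silent.** Pre-post correlation ρ from 0.3 to 0.8; ratio r of post-test SD to pretest SD of 0.8, 1 or 1.25; two-sided 95% intervals; no dropout; a common slope in both arms.

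**Step 1: what the planned test is.** In a generated 40 vs 20 data set, the group-by-time F was 1.3176 and the squared t on change scores was also 1.3176. The two tests are the same.

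**Step 2: variances.** With pretest SD = 1 and post-test SD = r, per participant:

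- Change score: V_c = 1 + r² − 2ρr
- ANCOVA: V_a = r²(1 − ρ²), multiplied by 1 + 1/(N − 4) = 1 + 1/56 = 1.018 for the cost of estimating the slope
- Before that cost, V_c − V_a = (1 − ρr)². This is never negative and is zero only when the slope ρr equals 1.

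Each variance is multiplied by 1/40 + 1/20 = 0.075. The half-width is t × √(0.075 V)/r, in post-test SDs, with t = 2.0017 (58 df) for change and 2.0025 (57 df) for ANCOVA.

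Example, r = 1 and ρ = 0.5: V_c = 1.00; V_a = 0.75 × 1.018 = 0.763; reduction 24%. Half-widths are 2.0017 × √0.075 = 0.548 and 2.0025 × √(0.075 × 0.763) = 0.479.

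| r | ρ | Slope ρr | Net variance reduction | Half-width, change | Half-width, ANCOVA |
|---|---|---|---|---|---|
| 1 | 0.3 | 0.30 | 34% | 0.649 | 0.528 |
| 1 | 0.5 | 0.50 | 24% | 0.548 | 0.479 |
| 1 | 0.7 | 0.70 | 14% | 0.425 | 0.395 |
| 1 | 0.8 | 0.80 | 8% | 0.347 | 0.332 |
| 0.8 | 0.3 | 0.24 | 49% | 0.738 | 0.528 |
| 0.8 | 0.5 | 0.40 | 42% | 0.628 | 0.479 |
| 0.8 | 0.7 | 0.56 | 36% | 0.494 | 0.395 |
| 0.8 | 0.8 | 0.64 | 35% | 0.411 | 0.332 |
| 1.25 | 0.3 | 0.38 | 20% | 0.590 | 0.528 |
| 1.25 | 0.5 | 0.63 | 9% | 0.502 | 0.479 |
| 1.25 | 0.7 | 0.88 | 0% | 0.395 | 0.395 |
| 1.25 | 0.8 | 1.00 | −2% | 0.329 | 0.332 |

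With equal SDs, the change-score analysis would need about 91, 79 or 69 participants at ρ = 0.3, 0.5 or 0.7 to match ANCOVA on 60 (60 × V_c/V_a).

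**Step 3: simulation.** With 40,000 trials per setting at 40 vs 20, both estimators were unbiased within 0.002 SD and coverage was 94.7% to 95.2%. At r = 1 the ANCOVA-to-change variance ratios were 0.660, 0.763, 0.872 and 0.916, in line with the table.

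**Step 4: the same loss seen through baseline imbalance.** The SE of the pretest difference is √0.075 = 0.274 SD. A difference of at least 0.3 SD in either direction therefore has probability 0.27 (z = 0.3/0.274 = 1.095). With equal SDs, a 0.3 SD imbalance shifts the change-score estimate by (1 − ρ) × 0.3 = 0.21, 0.15 or 0.09 SD at ρ = 0.3, 0.5 or 0.7. ANCOVA removes that shift on average.

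**Step 5: slopes that differ by arm.** Set the pretest variance to 1 and the residual variance to s. The variance using slope b is (s + (b_V − b)²)/40 + (s + (b_C − b)²)/20, where b_V and b_C are the VR-JIT and control slopes. A common-slope ANCOVA uses b = (2b_V + b_C)/3; the change score uses b = 1. The finite-sample cost is left out here.

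| b_V | b_C | s | ANCOVA | Change | Ratio |
|---|---|---|---|---|---|
| 0.3 | 0.8 | 1 | 0.08125 | 0.08925 | 0.91 |
| 0.6 | 1.4 | 1 | 0.09100 | 0.08700 | 1.05 |
| 0.4 | 1.3 | 1 | 0.09525 | 0.08850 | 1.08 |
| 0.4 | 1.3 | 0.36 | 0.04725 | 0.04050 | 1.17 |

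In this setting, ANCOVA can lose only if the slope exceeds 1 in at least one arm.

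**The case against.** The strongest reply is that nothing here is an error. The planned contrast is unbiased, has correct coverage and answers the hypothesis as worded. That is right, and the point is one of efficiency only.

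The size of the benefit also cannot be fixed from the documents. The same kind of interview is repeated within about five weeks, so ρ could be high and the gain small. Against that, the amendments allow telephone and post-release post-tests, which could lower ρ. Neither can be settled in advance, which favours an analysis that estimates the slope.

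Other objections stand in part:

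- The imbalance argument is not a second harm. It is already contained in the change-score variance and its interval.
- Section 13.0 names no method for H5's first step, so it is an inference that H5 inherits the H2 model.
- The 2% worst case holds only for a common slope. With strongly different slopes and 2:1 allocation the loss can be larger (Step 5), but such patterns are extreme.
- The protocol describes itself as otherwise the same as the 150-person companion study, HUM00155161, so changing H2 here alone could hinder comparison. Reporting the change-score contrast as well would meet this.
- Naming an estimate and interval, and reporting the correlation and SDs, could be done under RM-ANOVA too. That is true, and those items are worth adding whichever model is kept.

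**Conclusion.** The concern holds. The H2 analysis is valid, but it generally gives a wider interval than the same data allow. For the assumed correlations of 0.3 to 0.8 and a common slope, the net variance reduction from ANCOVA is 8% to 34% with equal SDs and 35% to 49% if the post-test SD is 0.8 times the pretest SD. If it is 1.25 times, the range is a 20% reduction to a 2% loss, the loss arising where the slope is 1. None of these correlations or SDs comes from the documents, so the range is the result and no single figure in it should be relied on. The change is worth making because it is free and because the pilot's declared output for H2 is an effect size.

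"Valid" here presumes that group by time is the term tested. The plan does not say so. The group main effect would average pretest and post-test and recover about half the effect (0.30 of a true 0.60 SD in simulation).

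**What to change.** In Section 13.0, restate the H2 analysis as ANCOVA: post-test (T2) interview score regressed on arm and pretest (T1) score. Name the adjusted arm difference at T2, with its 95% CI, as the H2 effect estimate. Also report the observed pre-post correlation and both SDs, so that the next trial can be sized from them.

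ANCOVA, like RM-ANOVA, uses only participants with a post-test. A constrained longitudinal mixed model with a common baseline mean, fitted by maximum likelihood, is an acceptable alternative that also keeps those with a pretest only. A site term is optional. The change-score contrast can be reported alongside for comparison with the companion study; if so, name it as the group-by-time term.

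The cost is one or two sentences, with no new data and no added participants. The statistical price is about 2% in variance if the common slope is 1, and more only if slopes differ strongly between arms with at least one above 1.

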Objective 1. Evaluate whether SAU+VR-JIT, compared with SAU-only, enhances employment outcomes and reduces recidivism among this population (i.e., effectiveness). At the individual level, we *hypothesize* (*H*) that SAU+VR-JIT trainees, compared with SAU-only trainees, will have higher employment rates (*H*1), greater improvement in job-interview skills (*H*2), and reduced recidivism (*H*3) by six-month and twelve-month follow-up. At the system level, we hypothesize that SAU+VR-JIT will be more

cost-effective than SAU-only (*H4*). **Subobjective 1.** Explore whether use of the computerized VR-JIT system frees up SAU staff time for non-interview-practice-related vocational training, relative to SAU-only (system level).

Figure 1. We will test whether interviewing skills mediate the relationship between VR-JIT completion and employment outcomes.

[figure not shown]
Objective 2. Evaluate the mechanisms of employment outcomes and explore the mechanisms of recidivism.

Based on Corbiere's model [19], we hypothesize that interview-skill improvement and measured role-play interview performance will mediate the effect of interview training on

employment outcomes (H5; Figure 1). Also, we will explore whether employment and mental health outcomes mediate the relationship

between interviewing skills and recidivism at six-month and twelvemonth follow-up (Figure 2). We will

Figure 2. We will test whether employment outcomes mediate the relationship between interviewing skills and recidivism.

also explore if mental health and life stress mediate the relationship between employment status and recidivism at six- and twelve-month follow-up.

1.1 Virtual Reality Job Interview Training (VR-JIT). This is an immersive simulation that allows trainees to have a virtual conversation with, and influence the behavior of, a simulated character [45–47]. Our previous studies suggest that virtual reality simulation training is engaging, and as a result, trainees will practice willingly for hours [27–30]. The VR-JIT simulation far exceeds typical interview training by combining video, speech recognition, and nonbranching logic (described below) to create an interactive environment in which trainees

encounter complex social cues and realistic interpersonal exchanges with a virtual hiring manager.

VR-JIT was designed as part of a collaborative partnership between SIMmersion LLC and our research team to improve interview skills using behavioral-learning principles

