At a ratio of 2:1(VR-JIT:Control) vocational villagers will be informed whether they are active in the Intervention Group or Control Group. The Control Group will continue their educational services as usual. MDOC will share the consented villager's recruitment information, such as their reading level, COMPAS score, etc., with UM research staff. They will do this via REDCap or MBox, both encrypted and secruite websites, or via UM phone, or in person with UM research staff.

D.3 Study Visit 3: Training Orientation with Village Participants

Participants randomized to the VR-JIT group will receive a 45-minute orientation to use the virtual training program. Study staff may be on site to facilitate this training session with Teachers. This session will be audiorecorded in order to monitor fidelity of the training. We will plan to audiorecord the first three sessions, and then randomly select approximately 20% of the following sessions to continue the fidelity monitoring process.

Villagers will train with the educational content.

Villagers will use 1 class period for orientation to learn to navigate and participate in the virtual interview.

D.4 Implementation of Intervention:

Villagers will complete up to 3 virtual job interviews per class period, or approximately 15 interviews over the course of the study.

D.5 Study Visit 3: Post Data Collection with Village Participants

All consented villagers in both groups (intervention and control) will complete a post-test employment survey, a practice interview with study staff that will be audio and video recorded, as well as some self-report measures. The practice interview can last up to 20 minutes. They will also be asked to complete a survey about their intervention and services-as-usual (SAU) use, and a survey assessing their acceptability and usability of the VR-JIT program, which should be around 10 minutes. This study visit should be approximately 60 minutes.

D.6 6-Month and 12-Month Follow-Up with Village Participants

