Surveys will be provided to N = 40 villagers randomized to VR-JIT to assess the acceptability and usability of VR-JIT. We will use items adapted from the Consolidated Framework for Implementation Research (CFIR) [43, 44]. Surveys adapted using CFIR will also be provided to the estimated N = 10 teachers from the Vocational Village (whom we will train to deliver VR-JIT) to assess provider views on VR-JIT acceptability, delivery strategies, and sustainability.

Exploratory Data

We will explore potential mechanisms for VR-JIT effectiveness (i.e., improved interview skills, attain a job), by first analyzing mediators (i.e., interview skills, self-confidence, and anxiety) and moderators using boot strapping (for mediators)⁴⁸ and linear regression (for moderators)⁴⁹. Second, we will explore potential mechanisms for a lack of improvement in interview skills and failure to attain a job) by examining group differences and associations between groups who did or did not have poor outcomes. Third, we will collect exploratory implementation data by interviewing vocational counselors and school administrators (N=10) about: 1) potential barriers and facilitators for VR-JIT implementation and scalability; and 2) how VR-JIT might reduce staff time required to deliver services. We will analyze this exploratory implementation data iteratively using thematic analysis and the constant comparative approach^{43, 44} to identify emergent themes regarding the barriers and facilitators of implementing VR-JIT.

14.0 Data Monitoring Plan to Ensure the Safety of Participants:

Data will be strictly monitored by the PI who regularly reviews testing and data management procedures to ensure protection of human subjects. We follow IRB and University of Michigan guidelines to minimize risk and report problems. We are required by our funding agency to report results annually. All data reported is de-identified prior to entry and analysis. We will initiate protocol revisions with the IRB when necessary. We have established a Data Safety and Monitoring Board to meet annually during the active recruitment phase of the study. The DSMB will review the research protocol and plans for data safety and monitoring, adverse events, risk management policies, and preliminary data analyssis. Members of the board include University of Michgan's [name], [name], Yale University's [name], and Department of Correction's [name].

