After the oral consent, the villager will attend Study Visits 1 and 2 one-on-one with study staff over a BlueJeans conference call in a semi-private room with a Vocational Village staff member to set up the phone call. Next, Village staff will provide the villagers with a copy of each survey. The villager will read the items and research staff will record them on an internal paper copy that they will later enter into the study's REDCap data base. There will be no survey data left in the Village as the participant will not be marking their answers down. Next, the mock job interview will be recorded via BlueJeans phone call, as originally agreed to on the consent form and from a previous amendment (of note, the collection of survey data will not be recorded on audio).

Randomization and intervention delivery will occur as previously approved.

Ame00102494

We have revised our inclusion criteria to expand recruitment to 36 years or older in order to meet our recruitment goals. We would also like to note that the corresponding study to this (HUM00155161) will be revising their recruitment age to 18-35 years old so the two study populations do not overlap.

We are also adding an additional contact plan for participants awaiting the 6-month and 12-month follow ups in order to keep open communication and remind them of their upcoming calls. We will be sending a postcard in an envelope in the mail approximately 4 times bewteen their follow up time points. For intervention participants, it will contain their intervention username and password as a reminder that they can log into the intervention if they so choose. While they were also given this information during their release, we think it would be best to send reminders whenever possible. Control participants will not receive their log in information until their 12 month follow up has been completed, however, they will still receive a postcard in an envelope. The postcard will be enclosed within an envelope so that username information is not displayed. However, if another person were to obtain the username/password, they will not have any access to any participant data or information as nothing is linked via the Simmersion website. All they will be able to do is access and use the virtual interview training.

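### The H5 mediation analysis names an interview count as exposure but begins with the randomised arms, and specifies no baseline adjustment for the non-randomised skill-to-employment path

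*Combined protocol and SAP*

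**What the plan says.** **Exposure.** Section 13.0 states H5 as mediation between "VR-JIT (number of completed virtual interviews) and employment outcomes (i.e., obtaining employment". The first analysis step is different: "we will test first for a significant SAU+VR-JIT impact on interview skills compared with SAU-only". The second is to "then check for treatment by mediator interaction [81", without defining treatment as count or arm. The third is a product of two coefficients with bootstrap intervals, again with no exposure coding. Objective 2 in section 1.0 uses broader terms for the exposure.

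**Window for the count.** None is given with H5. Section 6.0 D.4 ties the interviews to class periods before the post-test visit (D.5), and part E says study visits finish within about five weeks of enrolment. However, D.4 also describes roughly 15 interviews across the whole study. Amendment entry Ame00102494 adds a postcard for VR-JIT participants during follow-up: "it will contain their intervention username and password as a reminder that they can log into the intervention if they so choose". Controls get no log-in until their 12-month follow-up is complete.

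**Mediator.** H5 in section 13.0 speaks of improved skills. Objective 2 says that "interview-skill improvement and measured role-play interview performance will mediate the effect of interview training on" employment.

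**Adjustment.** No covariate is named for H5. The Exploratory Data paragraph plans a second mediation analysis, "analyzing mediators (i.e., interview skills, self-confidence, and anxiety) and moderators using boot strapping (for mediators", also without covariates. Adjusted proportions are mentioned only under H1, with no list. Baseline data are available: section 6.0 D.1 has a recorded practice interview, after which "they will complete some self-report measures on their anxiety, motivation, and self-efficacy". Under D.2 the corrections department shares recruitment data "such as their reading level, COMPAS score, etc., with UM research staff".

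**The concern.** Randomisation supports the comparison of arms on interview skill. It does not support the comparison of employment between people with higher and lower skill, which is the second coefficient in the product. A motivated person may interview better and also search harder for work. If nothing measured at baseline enters the model, that shared cause appears as mediation by skill.

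The exposure matters separately. A count is chosen by the participant, so using it gives up randomisation on the first path as well. Two analysts following the text could fit different exposures and different mediators and report different indirect effects. The pilot is meant to supply estimates for a later trial, so an undefined mediation estimate would be carried forward.

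**Working it through.** **The plan's own figure.** The plan gives only the allocation: 60 × 2/3 = 40 and 60 × 1/3 = 20, which agrees with section 4.0. It states no effect size, standard deviation or power for H5, so the rest is illustration on assumed inputs.

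**Inputs.** From the documents: 40 and 20 participants, and 25% employed within 12 months (section 2.2). Assumed:
- arm effect on skill d = 0.5 or 0.8 SD
- pre-post correlation r = 0.5
- a confounder u that raises the log-odds of employment by 0.5 or 1.0 per SD
- a motivation scale that measures u with reliability 0.7
- no true effect of skill on employment

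With 25% employment at average u, those log-odds equal s = 9.2 or 17.3 percentage points of employment per SD of u (average logistic slope over a normal u).

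**Formula.** False indirect effect = d × k × s. Here k is the coefficient of u on the mediator, given whatever else is in the model. Let u load L0 on pretest and L1 on post-test.
- Post-test, unadjusted: k = L1
- Change score, unadjusted: k = (L1 − L0) / (2(1 − r))
- Post-test adjusted for pretest: k = (L1 − r·L0) / (1 − r²)
- Post-test adjusted for motivation: k = 0.3·L1 / (1 − 0.7·L1²) = 0.15/0.825 = 0.182 for L1 = 0.5
- Both, equal-acting confounder (L0 = L1 = 0.5): k = 0.15/(0.825 + 0.325) = 0.130
- Both, gain-driving confounder (L0 = 0, L1 = 0.5): k = 0.15/(0.825 − 0.25) = 0.261

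Results in percentage points. The low end is d = 0.5 with s = 9.2; the high end is d = 0.8 with s = 17.3.

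| Mediator model | Equal-acting | Gain-driving |
|---|---|---|
| Post-test, unadjusted | k 0.50: 2.3 to 6.9 | k 0.50: 2.3 to 6.9 |
| Change score, unadjusted | k 0: 0 | k 0.50: 2.3 to 6.9 |
| Post-test + pretest | k 0.333: 1.5 to 4.6 | k 0.667: 3.1 to 9.2 |
| Post-test + motivation | k 0.182: 0.8 to 2.5 | k 0.182: 0.8 to 2.5 |
| Post-test + both | k 0.130: 0.6 to 1.8 | k 0.261: 1.2 to 3.6 |

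Simulation of 40:20 trials (20,000 per setting) gave the same values within simulation error. In the equal-acting case the bootstrap interval excluded zero in 6 to 28% of trials for the unadjusted post-test score, and in 3 to 7% with both covariates (5 to 9% if gain-driving). If the gain-driving loading is 0.3 rather than 0.5, the unadjusted bias is 1.4 to 4.1 and 0.6 to 1.8 with both.

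The most favourable case for pretest is a confounder that is baseline skill itself. A separate simulation of that case gave a false indirect effect of 0.09 to 0.47 log-odds unadjusted and about zero adjusted for pretest.

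**True mediation, no confounding.** If employment depends on skill level, an unadjusted change score recovers (1 − r)/(2(1 − r)) = 0.50 of the effect, whatever r is. If it depends on gain, an unadjusted post-test score recovers 1 − r: 0.50 at r = 0.5, 0.7 at r = 0.3, 0.3 at r = 0.7. Post-test score adjusted for pretest recovers both, because gain is a linear combination of the two scores. Simulation gave 4.88 (level) and 4.91 (gain) against a true 4.85 points.

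**Exposure.** With the count stopped at post-test, count and arm carry similar confounding bias (2.1 to 7.2 against 2.3 to 7.0 points). If the gain comes from being in the arm rather than from each interview, the count recovers 3.52/4.92 = 72% of the indirect effect. Arm recovers it either way.

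**Events.** 60 × 0.25 = 15 employed. Arm, post-test, pretest and one covariate make four coefficients: 15/4 = 3.8 events each, or 15/5 = 3.0 with the planned interaction. If the job-offer rates in section 2.6 applied (other populations), events would be 40 × 0.48 + 20 × 0.14 = 22.0 to 40 × 0.54 + 20 × 0.25 = 26.6, giving 5.5 to 6.7 and 4.4 to 5.3.

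**The case against.** The natural reading after step one is that arm enters throughout, and sections D.4, D.5 and part E suggest a count from the in-prison phase. Both are fair. They make the fix a clarification of the likely intent, but H5 itself says count and gives no window. H1's multiple logistic regression shows that covariate adjustment of employment is contemplated; it lists none and does not extend to H5.

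The change score has a real case. If gain drives employment and the confounder is stable, it recovers 1.01 to 1.02 of the truth, while the post-test score adjusted for pretest and motivation gives 1.15 to 1.27. It does badly if employment depends on level or if the confounder drives the gain. It therefore belongs as a sensitivity analysis.

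Three stronger readings are tempting but unsupported:
- **The choice of mediator alone halves or doubles the result.** Halving depends on whether level or gain matters, and the documents do not settle that. An estimate of about twice the truth needs strong confounding as well; without it, a post-test score adjusted for baseline gives 1.01 to 1.03 times the truth when employment depends on level.
- **Late log-ins reverse the sign of the count-employment relation.** H5 lists no test of that relation, and nothing says late log-ins enter the count. The effect rests on assumed differences in late use and vanishes if late use does not differ by employment.
- **H5 stops if step one is not significant.** The steps are listed in order, but no stopping rule is stated.

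**Conclusion.** The point holds. H5 leaves its exposure unresolved between count and arm, and specifies a product of coefficients with no baseline adjustment on a path that is not randomised. Run that way with a post-test mediator, it would show about +2 to +7 percentage points of mediation where none exists, under the inputs above. Two baseline measures already collected reduce this to about +0.6 to +1.8, or +1.2 to +3.6 if the confounder drives the gain. Pretest alone is not enough and increases the bias in the second case.

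The sizes depend on the assumed confounder strength, loadings, correlation and reliability. A stable confounder that the motivation scale misses leaves +1.5 to +4.6 even after adjustment. T1 to T3 are not defined in the documents; I take T2 as the post-test from H2. H5 is a secondary, mechanistic hypothesis in a 60-person pilot, and H1 to H3 are unaffected. Severity: consider.

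**What to change.** In section 13.0:
- State randomised arm as the exposure for every H5 step, including the interaction.
- Name the post-test interview score as the mediator. Adjust the mediator and outcome models for pretest score and one prespecified baseline covariate already collected, such as motivation. Report the change-score mediator as a sensitivity analysis.
- Confine any dose-response analysis to the VR-JIT arm, counting interviews completed before each participant's post-test, and label it secondary and non-randomised.
- Use the same model for H5 and for the interview-skill mediation in the Exploratory Data paragraph, label it exploratory, and acknowledge residual confounding.
- Use a risk-difference or penalised logistic outcome model, because events per coefficient are few.

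The cost is a few sentences and standard software, with no new data. The interval will be wide: in simulation, one covariate beyond pretest raised the spread of the skill coefficient from 0.38 to 0.41, about 8%.
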